**Table D1 Summary of International Myeloma Working Group-Uniform Response Criteria (IMWG-URC) (cont'd)**

Response Subcategory a	Response Criteria
-----------------------------------	-------------------

Sources: [Blade 1998](#); [Durie 2006](#); [Rajkumar 2011](#).

CR = complete response; sCR = stringent complete response; FLC = free light chain; PD = progressive disease; PR = partial response; SFLC = serum free light chain; VGPR = very good partial response.

- a Subjects with measurable disease in both serum (SPEP) and urine (UPEP) at study entry are required to meet response criteria in both UPEP and SPEP in order to qualify for a PR or better. Conversely, it should be noted that criteria for progressive disease only needs to be met, and confirmed, in one parameter.
- b All response categories (CR, sCR, VGPR, PR) require two consecutive assessments made at any time before the institution of any new therapy, as well as no known evidence of progressive or new bone lesions if radiographic studies were performed. Radiographic studies are not required to satisfy these response requirements. Bone marrow assessments are not required to be confirmed by repeat testing.
- c Presence/absence of clonal cells is based on the  $\kappa/\lambda$  ratio. An abnormal  $\kappa/\lambda$  ratio by immunohistochemistry and/or immunofluorescence requires a minimum of 100 plasma cells for analysis. An abnormal ratio reflecting presence of an abnormal clone is  $\kappa/\lambda$  of  $> 4:1$  or  $< 1:2$ .
- d Response criteria for all categories and subcategories of response except CR and VGPR are applicable only to patients that have “measurable” disease defined by at least one of SPEP  $\geq 1.0$  g/dL or UPEP  $\geq 200$  mg per 24 hours; except for assessment of sCR, CR, or VGPR, patients with measurable disease restricted to SPEP will need to be followed only by SPEP. Correspondingly, patients with measurable disease restricted to UPEP will need to be followed only by UPEP.
- e Determination of PD based on M-protein, hypercalcemia, or FLC while on study requires two consecutive assessments made at any time before classification of progressive disease and/or the institution of new therapy. Serum M-component increases of  $\geq 1$  g/dL are sufficient to define progression if starting M-component is  $\geq 5$  g/dL.
- f Plasmacytomas: A definite increase in the size is defined as a  $\geq 50\%$  increase as measured serially by the sum of the products of the cross-diameters of the measurable lesion. A plasmacytoma is considered measurable if the longest diameter is at least 1 cm and the product of the cross diameters is at least 1 cm^2. Plasmacytomas of lesser size will be considered nonmeasurable.
- g The requirement for bi-directional measurements will only be applied to plasmacytomas.
- h The plasmacytoma specifications for PD are based on the sponsor’s interpretation of the IMWG-URC and practical considerations for study execution.

Approved

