Treatment regimen(s):	Oral oprozomib taken Days 1–5 and 15–19 or Days 1, 2, 8, 9, 15, 16, 22, and 23, pomalidomide taken on 21 of 28 days, and oral dexamethasone taken on Days 1, 2, 8, 9, 15, 16, 22, and 23
Inclusion criteria:	
Disease Related
 

Multiple myeloma that is primary refractory, relapsed and refractory, or intolerant after at least 2 lines of standard therapy for multiple myeloma including:

≥ 2 consecutive cycles of both bortezomib and lenalidomide or thalidomide (alone or in combination)

In the dose-expansion portion of the study only: In addition to the above, treatment with adequate alkylator therapy, defined as:

High-dose melphalan or other alkylating agent as conditioning for autologous or allogeneic stem cell transplant (SCT), or

≥ 6 cycles of induction therapy, or

Progressive disease after ≥ 2 cycles

Measurable disease as indicated by 1 or more of the following:

Serum M-protein ≥ 500 mg/dL

Urine M-protein ≥ 200 mg/24 h

Only for subjects without measurable M-protein by serum protein electrophoresis (SPEP) and urine protein electrophoresis (UPEP), involved free light chain (FLC) concentration ≥ 10 mg/dL provided serum free light chain (SFLC) ratio is abnormal

Disease progression on or within 60 days of completion of the last therapy, or intolerance to bortezomib if received as their last therapy

Patients who received bortezomib as their last therapy who were not refractory but developed bortezomib intolerance, as defined by the development of Grade 2 peripheral neuropathy with pain or ≥ Grade 3 peripheral neuropathy after ≥ 2 consecutive cycles, are eligible

Prior carfilzomib is allowed if a subject was not removed from carfilzomib therapy due to toxicity, unless approved by the Sponsor's study medical monitor.

 
Demographic
 

Males and females ≥ 18 years old

Eastern Cooperative Oncology Group (ECOG) Performance Status of 0–2

 
Laboratory
 

Adequate hepatic function, with bilirubin ≤ 1.5 times the upper limit of normal (ULN) in the absence of Gilbert's disease or hemolysis, and alanine aminotransferase (ALT) and aspartate aminotransferase (AST) ≤ 3 times ULN

ANC ≥ 1500/mm^3. Screening ANC should be independent of myeloid growth factor support for at least 1 week or 2 weeks for pegylated growth factors.

Hemoglobin ≥ 8.0 g/dL. Patients may receive red blood cell (RBC) transfusions or receive erythropoietin or darbepoetin alfa in accordance with institutional guidelines up to 1 week before Screening.

Platelet count ≥ 75,000 mm^3. Patients should not have received platelet transfusions for at least 1 week before Screening.

Uric acid, if elevated, must be correct to within laboratory normal range before dosing

Calculated or measured creatinine clearance (CrCl) ≥ 30 mL/min calculated using the formula of Cockcroft and Gault <math>[(140 - \text{age}) \times \text{mass (kg)}] / (72 \times \text{serum creatinine mg/dL})</math>. Multiply result by 0.85 if female.

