Serum free light chain assay and kappa:lambda (K/ $\lambda$ ) ratio will be conducted according to the schedule outlined in the Schedule of Assessments, [Appendices A1, A2, B1, and B2](#). Only in subjects without measurable serum and urine M-protein levels (serum M-protein  $< 0.5$  g/dL or urine M-protein  $< 200$  mg/24 hours) at Baseline will SFCLC assays be used to determine eligibility and response. In subjects with measurable SPEP and/or UPEP, SFCLC may be used in conjunction with those assessments to determine response per disease response criteria but only SPEP and/or UPEP will be used to determine eligibility.

All response categories (CR, sCR, VGPR, PR, MR, PD) require 2 consecutive assessments made at any time before the institution of any new therapy. All subjects will be followed until disease progression (confirmed by 2 consecutive measurements that are also verified by the **Sponsor's** medical monitor prior to treatment discontinuation), unacceptable toxicity, or withdrawal of consent, whichever occurs first.

Disease progression will be determined and confirmed with the medical monitor by two consecutive assessments using the IMWG-URC ([Appendices A1, A2, B1, and B2](#)).

Approved

Serum M component increases of  $\geq 1.0$  g/dL are sufficient to define progression if the starting component is  $\geq 0.5$  g/dL according to these criteria. However, it is understood from these criteria that a single measurement is adequate in cases of clear increased bone marrow plasma cell percentage, development of new or worsened bone lesions from a skeletal survey, or development of new or worsened soft tissue plasmacytomas.

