#### 14.5.1.2 Efficacy Population

For this study, the efficacy population is equivalent to the safety population.

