### 14.5.2 EFFICACY ANALYSES

Overall response rate is defined as the proportion of subjects with a best response of sCR, CR, VGPR, or PR as determined by investigator according to the IMWG-URC.

Clinical benefit rate is defined as the proportion of subjects with a best response of PR or better according to IMWG-URC or a best response of MR according to the EBMT criteria, as determined by the investigator. A point estimate and 95% exact binomial confidence interval (CI) will be calculated for both ORR and CBR for all subjects treated at the RP3D (during dose escalation and expansion for each schedule). A descriptive summary of ORR and responses will also be provided by dose cohort.

Progression-free survival and **duration of response (DOR)** will be listed for all subjects in the efficacy population by dose cohort level and schedule.

Approved

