**APPENDIX C RESPONSE CRITERIA FOR MULTIPLE MYELOMA**

**Table D1 Summary of International Myeloma Working Group-Uniform Response Criteria (IMWG-URC)**

Response Subcategory a	Response Criteria
sCR b	
 
Negative immunofixation on the serum and urine and
 
Disappearance of any soft tissue plasmacytomas and
 
< 5% plasma cells in bone marrow and
 
Normal SFLC ratio and
 
Absence of clonal cells in bone marrowc
 

CR b	
 
Negative immunofixation on the serum and urine and
 
Disappearance of any soft tissue plasmacytomas and
 
< 5% plasma cells in bone marrow
 

VGPR b, d	
 
Serum and urine M-protein detectable by immunofixation but not on electrophoresis or
 
≥ 90% reduction in serum M-component with urine M-component < 100 mg per 24 hours                             
 
If the serum and urine M-protein are not measurable, a decrease of > 90% in the difference between the involved and uninvolved sFLC levels is required in place of the M-protein criteria
 
 
 

PR b, d	
 
≥ 50% reduction of serum M-protein and reduction in 24-hour urinary M-protein by ≥ 90% or to < 200 mg per 24 hours
 
If the serum and urine M-protein are not measurable, a decrease ≥ 50% in the difference between involved and uninvolved FLC levels is required in place of the M-protein criteria.
 
If present at baseline, a ≥ 50% reduction in the size of soft tissue plasmacytomas is also requiredd, e
 

Stable	
 
Not meeting criteria for CR, VGPR, PR, or PD
 

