**Table D2 Definition of Minimal Response per EBMT Criteria**

Minimal Response	
Response Subcategory	Response Criteria
MR a	≥ 25 but < 49% reduction in serum M-protein and a 50–89% reduction in 24-hour urinary M-protein, which still exceeds 200 mg per 24 h
	If the serum and urine M-protein are not measurable, a decrease of 25%–49% in the difference between involved and uninvolved FLC levels is required in place of the M-protein criteria.
	For patients with nonsecretory myeloma only, 25–49% reduction in plasma cells in a bone marrow aspirate and on trephine biopsy, if biopsy is performed
	25–49% reduction in the size of soft tissue plasmacytomas (by radiography or clinical examination)

Sources: [Bladé 1998](#); [Kyle 2009](#).

EBMT = European Group for Blood and Marrow Transplantation; FLC = free light chain; MR = minimal response.

a The response category MR requires 2 consecutive assessments made at any time before the institution of any new therapy, as well as no known evidence of progressive or new bone lesions if radiographic studies were performed. Radiographic studies are not required to satisfy these response requirements. Bone marrow assessments are not required to be confirmed by repeat testing.

Approved

**APPENDIX D EUROPEAN ORGANIZATION FOR RESEARCH AND  
TREATMENT OF CANCER (EORTC) CORE MODULE (QLQ-C30) AND  
EORTC MULTIPLE MYELOMA MODULE (QLQ-MY20)**

Subjects should be instructed to fill out the EORTC QLC-C30 (Version 3) and EORTC QLC-MY20 questionnaires to the best of their abilities. The study staff will be responsible for confirming that the subject has completed the questionnaires.

Citations for the EORTC QLQ-C30 and the EORTC QLQ-MY20 are provided in the Reference List ([Aaronson 1993](#); [Fayers 2001](#); [Cocks 2007](#)).

Approved

---

CONFIDENTIAL

Onyx Therapeutics  
Oprozomib ER Tablets

Clinical Study Protocol No. OPZ007  
Page 133 of 223

**APPENDIX E NEUROTOXICITY SUBSCALE OF THE GYNECOLOGIC  
ONCOLOGY GROUP'S FUNCTIONAL ASSESSMENT OF CANCER THERAPY  
(FACT/GOG-NTX4 [VERSION 4])**

Subjects with neurotoxicities should be instructed to fill out the FACT/GOG-Ntx4 (Version 4) to the best of their abilities. The study staff will be responsible for confirming that the subject has completed the questionnaire.

Approved

---

CONFIDENTIAL

Onyx Therapeutics  
Oprozomib ER Tablets

Clinical Study Protocol No. OPZ007  
Page 134 of 223

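### Subjects may enter with serum M-protein of 0.5 g/dL, but Table D1 footnote d allows PR only from 1.0 g/dL, so PR scoring of some eligible subjects is barred or ambiguous.

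*Protocol*

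**What the plan says.** **Entry.** The Synopsis and Section 6.1 require one or more of three markers. The first is "Serum M-protein ≥ 500 mg/dL". The second is urine M-protein of at least 200 mg/24 h. The third, open only to subjects measurable by neither SPEP nor UPEP, is "involved free light chain (FLC) concentration ≥ 10 mg/dL provided serum free light chain (SFLC) ratio is abnormal".

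**Section 11.3.** "Only in subjects without measurable serum and urine M-protein levels" are SFLC assays used for eligibility and response. The section sets the limits at 0.5 g/dL for serum and 200 mg/24 h for urine.

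**Appendix C, Table D1.** The PR row asks for a serum M-protein fall of at least 50%, together with a urine condition. If M-protein is not measurable, a fall of at least 50% "in the difference between involved and uninvolved FLC levels is required in place of the M-protein criteria". Footnote d is attached to this row: "Response criteria for all categories and subcategories of response except CR and VGPR are applicable only to patients that have" SPEP of at least 1.0 g/dL or UPEP of at least 200 mg/24 h.

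**Appendix C, Table D2.** The serum part of MR is "≥ 25 but < 49% reduction in serum M-protein". Footnote d is not attached to it.

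**Analysis.** Protocol 14.5.2: a point estimate and exact 95% interval "will be calculated for both ORR and CBR for all subjects treated at the RP3D". Protocol 14.5.1.2: "For this study, the efficacy population is equivalent to the safety population". SAP Section 4 also keeps all treated subjects, and SAP 7.5.1 refers to IMWG-URC without giving a threshold.

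**The concern.** The serum limit in footnote d is twice the entry limit, while the urine limit is the same throughout. Nothing in either document says that some eligible subjects are meant to be unscorable for PR, and neither provides a response-evaluable set that would remove them from the denominator.

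ORR is a secondary endpoint, and preliminary activity is one of several inputs to the RP3D. Response is judged by investigators at about 35 planned sites. Depending on the reading used, ORR is either pulled down or scored inconsistently.

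CBR is affected through the same subjects. A serum fall of 50% or more that is barred from PR does not fit MR either, because the MR serum band ends below 49%.

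**Working it through.** **1. Units.** 500 mg/dL ÷ 1000 = 0.5 g/dL, against 1.0 g/dL in footnote d. The urine limit is 200 mg/24 h in the inclusion criteria, Section 11.3 and footnote d.

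**2. Who is caught.**

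| Eligible subject | Section 11.3 | Table D1, PR row | Footnote d |
|---|---|---|---|
| SPEP 0.5 to <1.0 g/dL, UPEP <200 mg/24 h | measurable by SPEP | M-protein rule; FLC rule only if not measurable | PR not applicable |
| FLC only | scored by SFLC | FLC rule, fall of at least 50% | no FLC route |

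For the first group three readings are open:
- PR by M-protein, following 11.3.
- No PR, following footnote d.
- PR by FLC, if footnote d's limit decides what counts as not measurable. Section 11.3 allows SFLC only alongside SPEP or UPEP once either is measurable.

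**3. The plan's own figure.** Protocol 14.7 and SAP 2.4 state about 94% for at least 7 responses among 26 subjects at a true ORR of 40%. P(Bin(26, 0.40) ≥ 7) = 0.944, so the figure reproduces.

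**4. Effect if footnote d is applied as written.** Let k be the number of the 26 subjects barred from PR, and v the share of responders who reach VGPR or better. Both are assumptions, since the documents give neither. Then

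X = Bin(26 − k, 0.40) + Bin(k, 0.40v), and expected ORR = 0.40 × (26 − k + kv)/26.

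| k | P(X ≥ 7), v = 0 | P(X ≥ 7), v = 0.75 | Expected ORR, v = 0 | Expected ORR, v = 0.75 |
|---|---|---|---|---|
| 0 | 94.4% | 94.4% | 40.0% | 40.0% |
| 1 | 92.6% | 94.0% | 38.5% | 39.6% |
| 3 | 87.6% | 93.0% | 35.4% | 38.8% |
| 6 | 75.0% | 91.3% | 30.8% | 37.7% |

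For example, k = 6 and v = 0 gives 0.40 × 20/26 = 30.8%.

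**5. Effect on one observed result.** Ten responders of 26 is 38.5% (exact 95% CI 20.2 to 59.4). If two of them were PRs that footnote d disallows, the result is 8 of 26, or 30.8% (14.3 to 51.8).

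**6. Two smaller slips in Section 11.3.**
- The parenthesis defining non-measurable disease joins the serum and urine limits with *or*, where the inclusion criterion has *and*. The next sentence in 11.3 largely resolves this.
- The rule that a 1 g/dL rise is enough for PD starts from 0.5 g/dL in 11.3 and from 5 g/dL in footnote e. The usual rule is a 25% rise from the lowest value, with at least 0.5 g/dL absolute. A 1.0 g/dL rise is 25.0% of 4.0, 24.4% of 4.1, 22.2% of 4.5 and 20.4% of 4.9. The texts therefore differ only when the start is below 5 g/dL and the lowest value is above 4.0 g/dL. A serum responder starting below 5 g/dL has a lowest value below 2.5 g/dL, so a 1.0 g/dL rise exceeds 40% and is PD under both texts. DOR in serum responders is untouched; only PD calls and listed PFS in some non-responders can change.

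**The case against.** The strongest reply is that the restrictive reading is not the natural one. Section 11.3 uses 0.5 g/dL for response as well as eligibility, and footnote a ties measurable disease to study entry. Barring FLC-only subjects would make the PR row's own FLC rule meaningless. This makes it plausible that many investigators would score PR in these subjects. It does not remove footnote d, which is explicit, sits on the PR row and is not overridden anywhere. The FLC-only limb is the weaker of the two, but there the table contradicts itself.

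It can also be said that ORR is defined by IMWG-URC, so if footnote d reproduces that standard, barring PR is the endpoint and not a bias. The source is not available here, so this cannot be settled. It would still leave the trial admitting subjects whose PR cannot count while keeping them in the denominator, with 11.3 saying otherwise.

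Table D2 also asks for a urine fall to a level still above 200 mg/24 h, which a subject below that level at entry cannot literally meet. That is a separate question about MR and does not change how footnote d reaches CBR.

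The limits on impact stand. The number affected is unknown, the low figures need 6 of 26 affected and none of their responders reaching VGPR, and no decision rule hangs on 7 responses. PD is confirmed with the medical monitor. SAP 2.1 gives reasons other than response for cancelling Phase 3, and Amendment 3 was not implemented.

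**Conclusion.** The concern holds. The current text contains two serum limits for measurable disease, and nothing reconciles them. Footnote d taken literally turns a fall of at least 50% in an eligible subject into a non-response. Read against 11.3, the same subject may be scored in more than one way.

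The contradiction itself rests on no assumption; its size does. One affected subject among 26 barely matters, and three or more begin to show if few responders reach VGPR. Zero effect is possible, and the plan's 94% is correct on its own terms. This should be fixed because it can misclassify a secondary endpoint and is simple to remove. The *or*/*and* slip and the PD starting value are minor.

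**What to change.** Make footnote d's definition of measurable disease match the entry criteria: serum M-protein of at least 0.5 g/dL, or urine M-protein of at least 200 mg/24 h, or, when neither is measurable, involved FLC of at least 10 mg/dL with an abnormal ratio. Every eligible subject can then be scored for PR.

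In Section 11.3, change *or* to *and* in the parenthesis. Separately, reconcile the starting M-component of the absolute-rise PD rule between 11.3 and footnote e.

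The cost is wording only, with no new data and no more patients. Where responses have already been scored, check the PR calls in subjects who entered with SPEP from 0.5 to below 1.0 g/dL and UPEP below 200 mg/24 h, or by FLC only.

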**Table D2 Definition of Minimal Response per EBMT Criteria**

Minimal Response	
Response Subcategory	Response Criteria
MR a	≥ 25 but < 49% reduction in serum M-protein and a 50–89% reduction in 24-hour urinary M-protein, which still exceeds 200 mg per 24 h
	If the serum and urine M-protein are not measurable, a decrease of 25%–49% in the difference between involved and uninvolved FLC levels is required in place of the M-protein criteria.
	For patients with nonsecretory myeloma only, 25–49% reduction in plasma cells in a bone marrow aspirate and on trephine biopsy, if biopsy is performed
	25–49% reduction in the size of soft tissue plasmacytomas (by radiography or clinical examination)

Sources: [Bladé 1998](#); [Kyle 2009](#).

EBMT = European Group for Blood and Marrow Transplantation; FLC = free light chain; MR = minimal response.

a The response category MR requires 2 consecutive assessments made at any time before the institution of any new therapy, as well as no known evidence of progressive or new bone lesions if radiographic studies were performed. Radiographic studies are not required to satisfy these response requirements. Bone marrow assessments are not required to be confirmed by repeat testing.

Approved

**APPENDIX D EUROPEAN ORGANIZATION FOR RESEARCH AND  
TREATMENT OF CANCER (EORTC) CORE MODULE (QLQ-C30) AND  
EORTC MULTIPLE MYELOMA MODULE (QLQ-MY20)**

Subjects should be instructed to fill out the EORTC QLC-C30 (Version 3) and EORTC QLC-MY20 questionnaires to the best of their abilities. The study staff will be responsible for confirming that the subject has completed the questionnaires.

Citations for the EORTC QLQ-C30 and the EORTC QLQ-MY20 are provided in the Reference List ([Aaronson 1993](#); [Fayers 2001](#); [Cocks 2007](#)).

Approved

---

CONFIDENTIAL

Onyx Therapeutics  
Oprozomib ER Tablets

Clinical Study Protocol No. OPZ007  
Page 133 of 223

**APPENDIX E NEUROTOXICITY SUBSCALE OF THE GYNECOLOGIC  
ONCOLOGY GROUP'S FUNCTIONAL ASSESSMENT OF CANCER THERAPY  
(FACT/GOG-NTX4 [VERSION 4])**

Subjects with neurotoxicities should be instructed to fill out the FACT/GOG-Ntx4 (Version 4) to the best of their abilities. The study staff will be responsible for confirming that the subject has completed the questionnaire.

Approved

---

CONFIDENTIAL

Onyx Therapeutics  
Oprozomib ER Tablets

Clinical Study Protocol No. OPZ007  
Page 134 of 223

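### Table D2 caps minimal response on both serum and urine, so a subject measurable in both who reaches the PR level on only one marker is graded stable, and the clinical benefit rate can be understated

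*Protocol*

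**What the plan says.** Protocol Appendix C, Table D2, gives the M-protein rule for MR as "≥ 25 but < 49% reduction in serum M-protein and a 50–89% reduction in 24-hour urinary M-protein", and adds of the urine value "which still exceeds 200 mg per 24 h". Both conditions have an upper limit and they are joined by *and*.

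For PR, Table D1 asks for "≥ 50% reduction of serum M-protein and reduction in 24-hour urinary M-protein by ≥ 90" percent, or a fall of urine M-protein to under 200 mg/24 h. Footnote a to Table D1 says that subjects measurable in both serum and urine "are required to meet response criteria in both UPEP and SPEP in order to qualify for a PR or better". The Stable row takes everyone who meets no listed response category and has not progressed.

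Footnote d to Table D1 covers single-marker disease: "patients with measurable disease restricted to SPEP will need to be followed only by SPEP", with a matching rule for urine. Table D2 neither repeats nor cites it; its own footnote concerns confirmation.

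Protocol 14.5.2 counts a subject in CBR for PR or better under the IMWG-URC, or for "a best response of MR according to the EBMT criteria, as determined by the investigator". CBR at the RP3D is reported as a point estimate with a 95% exact binomial interval. The SAP lists CBR as a secondary objective (2.3.2) and clinical benefit as a secondary endpoint (3.2). Its efficacy section (7.5) covers only ORR and duration of response, and gives no rule for deriving MR.

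**The concern.** A response scale should be monotone: doing better on one marker, with the other unchanged, should never lower the grade. For subjects measurable in both serum and urine, Table D2 breaks this. Someone who passes the MR ceiling on one marker leaves the MR window, but cannot enter PR until the other marker also reaches the PR level. In between, the printed rules give stable disease.

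CBR is a secondary objective and endpoint, and its estimate and interval are all that the plan reports for it. The error runs one way, because subjects with real benefit are left out and none are added. ORR is not touched, because MR does not count towards it.

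**Working it through.** **Inputs.** MR window: Table D2. PR rule: Table D1 and its footnote a. Eligibility for urine M-protein (at least 200 mg/24 h): Protocol 6.1. Planned 26 subjects per schedule (6 at the MTD plus 20 in expansion), ORR 40% and at least 7 responses: Protocol 14.7.

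**The plan's own figure.** The only operating figure given for response is the probability of at least 7 responses among 26 at a true ORR of 40%. P(X ≥ 7 | n = 26, p = 0.40) = 0.944, which agrees with the stated 94%. MR does not enter it.

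**Literal grading, subject measurable in both markers.**

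| Serum fall | Urine, mg/24 h (fall) | PR? | MR? | Grade |
|---|---|---|---|---|
| 40% | 2000 to 600 (70%) | no | yes | MR |
| 60% | 2000 to 600 (70%) | no: urine | no: serum above ceiling | stable |
| 90% | 3000 to 600 (80%) | no: urine | no: serum above ceiling | stable |
| 40% | 2000 to 100 (95%) | no: serum | no: urine above ceiling and not over 200 mg | stable |
| 49.5% | 2000 to 600 (70%) | no | no: between 49% and 50% | stable |
| 40% | 3000 to 315 (89.5%) | no | no: between 89% and 90% | stable |
| 40% | 400 to 160 (60%) | no: serum | no: urine not over 200 mg | stable |

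VGPR does not rescue the third row: it needs urine M-protein under 100 mg/24 h, or none visible on electrophoresis. Rows 1 and 2 differ only in a better serum result, and so do rows 1 and 3 in substance, yet the grade falls.

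**Low baseline urine.** MR needs a urine fall of at least 50% and a residual above 200 mg/24 h. With baseline B, a 50% fall leaves at most B/2, so both can hold only if B/2 > 200, that is B > 400. Eligibility starts at 200. For B from 200 to 400 mg/24 h, MR by M-protein cannot be met. This matters when serum is also measurable; a urine-only subject who falls below 200 mg meets PR instead.

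**Effect on CBR.** Each subject moved from stable to MR adds 1/26 = 3.8 points. For illustration, 12/26 = 46.2% (95% exact interval 26.6 to 66.6) becomes 13/26 = 50.0% (29.9 to 70.1).

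**How many subjects.** The documents give neither the share measurable in both markers (q) nor the share of those whose best confirmed response lies in the gap (g). Both are assumptions here, q from 10% to 40% and g from 5% to 30%:

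- Low end: 0.10 × 0.05 = 0.5 points, or 26 × 0.005 = 0.13 subjects.
- High end: 0.40 × 0.30 = 12 points, or 26 × 0.12 = 3.12 subjects.

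**The case against.** *Response is the investigator's judgement, and CBR uses best response.* Nothing in this Phase 1b plan says that a program applies Table D2 literally, and a sensible investigator may call a mixed response MR. A subject with two earlier consecutive assessments inside the MR window also keeps MR. Both points stand and limit the size. They do not remove the defect: Protocol 11.3 sends investigators to Appendix C, and about 35 sites would each have to decide whether to depart from the printed rule.

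*The table carries the name of a published standard.* Whether the windows match the source cannot be checked from these documents. But the objectives and endpoints refer to modified EBMT criteria, so the protocol's own wording governs, and it can say how mixed responses are graded.

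*The 49% to 50% gap is a rounding edge.* Largely true. It is worth closing because it costs nothing, not because it will move CBR.

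*Serum-only disease.* A reader might infer that serum-only subjects fail both MR and PR, because they cannot show the urine fall in Table D2. The documents do not support this. PR accepts urine under 200 mg/24 h, which these subjects already have, so a serum fall of 50% or more is PR. Footnote d, which covers all categories except CR and VGPR, has them followed by serum alone, so a fall of 25% to under 49% is MR on a normal reading. What is left is a missing cross-reference.

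*Using Protocol Table 1 for the size.* CBR minus ORR there is 10.0, 11.1 and 26.7 points. Those figures come from Study 2011-001, whose MR definition is not given. They show that MR was recorded in that study, not how many subjects Table D2 would misgrade in this one.

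**Conclusion.** The point holds for subjects with measurable M-protein in both serum and urine. Read as printed, Table D2 leaves mixed responders in no response category, makes MR by M-protein unattainable at baseline urine of 200 to 400 mg/24 h, and leaves a sliver at a serum fall of 49% to under 50%. CBR can be understated by 3.8 points of 26 per affected subject. On the assumed shares above, the total is about 0.5 to 12 points; the true number cannot be found from the documents.

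Two stronger readings should be resisted. A reader might conclude that the reported CBR is wrong. The documents show only that it can be too low, for some subjects, if the rule is applied literally. A reader might also note that in the PR row "If present at baseline, a ≥ 50% reduction in the size of soft tissue plasmacytomas is also required", while the VGPR row has no such condition and the CR row has no light-chain condition, and infer that ORR is inflated. Table D1 is presented as a summary of a named standard that cannot be checked here, so the documents do not support changing those rows.

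ORR and the 94% figure are unaffected. CBR is a secondary, descriptive endpoint with no test and no role in the sample size, so this is a correction worth making rather than one the trial depends on.

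**What to change.** In the M-protein row of Table D2, define MR as PR or better not met, with a serum reduction of at least 25% and a 24-hour urine reduction of at least 50%, each required only for a marker measurable at baseline. Drop the upper limits and the residual-urine condition as bars to MR. Make the light-chain band 25% to under 50%. Keep the nonsecretory-marrow and plasmacytoma rows. Cite Table D1 footnote d under Table D2.

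Two details need a phrase each. With baseline urine below 400 mg/24 h, a fall to under 200 mg can satisfy PR on the urine side while being less than 50%, so that result should also count as meeting the MR floor. And footnote d takes measurable serum disease as at least 1.0 g/dL, while inclusion uses 500 mg/dL; the table should say which threshold applies.

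The cost is a few lines of appendix wording. For subjects already graded, it means checking the serum and urine values already collected for those measurable in both markers and graded stable. The investigator should confirm any change, so that the endpoint stays investigator-determined.
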